1 SUMMARY

Title:	Short versus long interval to loop ileostomy reversal after ileal pouch surgery in patients with ulcerative colitis (SLIRPS) trial
Research Hypothesis:	In patients with ulcerative or indeterminate colitis who undergo ileal pouch anal anastomosis and diverting loop ileostomy (IPAA) surgery a short interval to loop ileostomy reversal will result in differences in complications and quality of life compared to a long interval to loop ileostomy reversal.
Phase:	III
Study design:	Prospective, randomized, multicenter
Study population:	Adult patients with ulcerative colitis (UC) or indeterminate colitis (IC) who will undergo ileal j-pouch surgery.
Sample size:	126-152 patients
Treatment:	
Phase 1:
 
 Colorectal excision, ileal j-pouch, & diverting ileostomy surgery 
Phase 2:
 
 Diverting ileostomy closure surgery
Treatment duration:	Phase 1 will have a treatment duration of approximately 6 weeks that will begin after informed consent #1 is obtained and will end within 1 week of ileal j-pouch surgery. Phase 2 will have a duration of approximately 6 months and will begin after informed consent #2 is obtained.
Criteria for inclusion:	
 Signed informed consents. Man or woman between 18 and 64 years of age. UC or IC diagnosed by routine clinical, radiographic, endoscopic, and pathological criteria. Patient will be scheduled for non-emergent proctocolectomy or completion proctectomy with ileal j-pouch anal anastomosis

Timing of Ileostomy Closure after Ileal Pouch Surgery

	
(IPAA) and loop ileostomy (IPAA).
 
 • Clinical assessment of patient after IPAA surgery indicates that patient is suitable for early ileostomy reversal

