Secondary variables:	(1) Total number of postoperative complications per patient; (2) Percent of patients with complications; (3) Total number of stoma related complications per patient; (4) Health-related quality of life; and (5) IPAA functional outcomes (all at 6 months after randomization).
Statistical analysis:	
A Consort Diagram will be used to account for all patients screened for inclusion in the trial; those who were excluded and included and reasons for exclusion; those who were randomized; and those who were followed at each time point or who were lost to follow-up. The primary analysis will be by intention-to-treat, meaning that the patients will be analyzed by the group to which they were randomized. This means that patients randomized to the short interval closure group who have postoperative complications that delay closure will still be analyzed in the group to which they were randomized. Secondary analyses will be done per-protocol (analyzing patients who followed the protocol), and as-treated (analyzing patients by the treatment they actually received).
 
Patient baseline characteristics will be compared between the early and late closure groups using a chi-square test for categorical variables and a t-test for independent samples for normal continuous variables or a Wilcoxon two sample ranks test for non-normal continuous variables.
 
Complications will be reported using the Clavien-Dindo classification. Perioperative details in the two groups will be compared using the same methods as were used for comparing the

Timing of Ileostomy Closure after Ileal Pouch Surgery

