	
patient baseline characteristics.
 
The primary analysis will be comparing Comprehensive Complication index and overall complication rates up to 6 months postoperatively between the two randomized groups using a generalized linear model with a log-link function with group (short vs. long interval closure) and hospital as the independent variables. We will also include any patient baseline characteristics that remained unbalanced in spite of randomization. Secondary analyses will include a comparison of mean number of complications per patient using a zero-inflated Poisson model, and a comparison of severe complications (Clavien-Dindo Grade IIIa or higher) using the same methods as were used for the primary analysis. We will also compare the mean number of stoma related complications using a zero-inflated Poisson model. Since the quality of life scales are continuous variables measured over time, we will compare the early vs. late closure groups for these outcomes using linear mixed models.

Duration of study	Duration per patient will be approximately 7 months. The anticipated time of the overall study duration is approximately 18 months
Number of centres:	17-25 centers in United States

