Quality of life and functional outcomes of IPAA in patients with ulcerative colitis have been evaluated in retrospective studies. (Delaney 2003, Farouk 2000) The SF-12 is a validated quality of life measurement tool that has been used to evaluate patients who have undergone colorectal resection.

JUSTIFICATION AND OBJECTIVES OF THE CLINICAL TRIAL

Randomized prospective trials have evaluated the outcomes of standard (8 weeks) and decreased (8-13 day) intervals to defunctioning ileostomy reversal after rectal cancer surgery and have demonstrated superiority of decreased interval to closure. [Danielsen 2017; Alves 2008] The unique significance of our study is that it will focus on ulcerative colitis patients who undergo ileal pouch surgery with temporary defunctioning ileostomy.

This operation is performed on a minimum of 15 patients, with UC or IC, annually at University of Colorado Hospital and at the co-investigator centers. This surgery is performed by fellowship-trained and board certified colorectal surgeons at the University of Colorado.

Hypothesis: In patients with ulcerative or indeterminate colitis who undergo ileal pouch anal anastomosis and diverting loop ileostomy (IPAA) surgery* a short interval to loop ileostomy reversal will result in differences in complications and quality of life compared to a long interval to loop ileostomy reversal.

*For clarification, please see illustrations and images at end of this document

Aim #1: To compare the Comprehensive Complication Index (CCI), the incidence of postoperative complications, including total number of complications per patient, percent of patients with complications, and total number of ostomy-related complications per patient among IPAA patients who have their ileostomy reversed after a short interval compared to a long interval.

Aim #2: To compare the short vs. long interval groups on measures of health-related quality of life (SF-12) and IPAA functional outcomes

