7. PHASE 2 (day 7 to 12 or week 8-12): Ileostomy Closure:

- a. Early ileostomy closure will be performed at 7 to 12 days after IPAA.
- b. Late ileostomy closure will be performed 8 - 12 weeks after IPAA.
- c. The ileostomy closure surgical technique is at the discretion of the surgeon.
- d. CRF-5 (ileostomy reversal details) will be completed within 3 days of ileostomy reversal surgery.
- e. Endoscopic examination (optional): Rigid and/or flexible endoscopic examination of the IPAA may be performed per standard practice/standard of care, including non-study-related informed consent, at the discretion of the study surgeon following standard of care. (CRF-5)

8. PHASE 2 (day 7 – 12 to 6 months): Outcome assessment:

- a. The Comprehensive Complication Index and postoperative complications will be assessed and recorded by the study surgeon or trial assistant after review of the medical record, conversation with patient, and members of the care team (when appropriate). This assessment and documentation will begin immediately after randomization is performed and will be updated at 1-2 month intervals until 6 months after randomization. (CRF-6)
- b. Functional outcomes and quality of life (CRF-7): IPAA functional outcomes and quality of life (SF-12) will be assessed and recorded once at 6 months after ostomy reversal.

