9 RANDOMIZATION, DATA MANAGEMENT AND DATA MONITORING

The randomization of the patients and the processing and analysis of the data will be carried out by the lead study biostatistician ([name]) at University of Colorado. The randomization will be stratified by study site. Within each site, randomly selected block sizes of 2, 4, or 6 will be used so that the site investigators cannot predict beforehand the group to which the patient will be randomized.

Data collection will be performed using REDCap (Research Electronic Data Capture). REDCap is a secure web application for building and managing online surveys and databases. The software is available at no cost for REDCap Consortium Partners. The building of an online survey or database and the inputting of data can be done anywhere in the world over a secure web connection with authentication and data logging. The REDCap surveys and databases can be used by researchers from multiple sites and institutions. Confidentiality will be protected. REDCap is considered "Part 11 capable", meaning that the software has all the required features for compliance.

Timing of Ileostomy Closure after Ileal Pouch Surgery

We have built a REDCap database for this study using 8 forms per patient. These will include Form 1, Screening; Form 2, Pre-IPAA Data; Form 3, IPAA operative Details; Form 4, IPAA Assessment; Form 5, ostomy reversal details; Form 6, Complications; Form 7 – Functional Outcome & SF-12; Form 8, Adverse Events.

Study data for this study will be collected and stored using electronic records. Data captured will be entered in real time at each clinical site using web forms developed to replicate paper case report forms. All data will be created, modified, maintained, archived, retrieved and distributed by a computer system. The use of electronic records will increase the speed of data collection and exchange. This will reduce the manpower necessary to perform double-data entry from paper forms and transcription error. In addition, electronic records permit economical storage of study data and ease of accessibility and analysis. Data management and data quality systems will be built into the system.

Data quality using electronic records will ensure that data are attributable, legible, contemporaneous and original.

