group (short vs. long interval closure) and hospital as the independent variables. We will also include any patient baseline characteristics that remained unbalanced in spite of randomization. Secondary analyses will include a comparison of mean number of complications per patient using a zero-inflated Poisson model, and a comparison of severe complications (Clavien-Dindo Grade IIIa or higher) using the same methods as were used for the primary analysis. We will also compare the mean number of stoma related complications using a zero-inflated Poisson model. Since the quality of life scales are continuous variables measured over time, we will compare the early vs. late closure groups for these outcomes using linear mixed models.

DSMB interim analyses and early stopping rules for interim analyses

At their first meeting, the DSMB will decide how they wish to monitor the study. Typically, a DSMB will monitor all aspects of a study to ensure its scientific integrity, including patient screening and accrual, follow up, performance of individual centers, data acquisition and quality issues, adverse events, and outcomes. At the first meeting, we will also determine their desire in establishing formalized stopping rules. Any data presented by treatment group at the DSMB meeting will be blinded with regard to the identity of the comparison groups, and participating investigators (except for the study biostatistician) will not see any data broken down by treatment group during the course of the trial.

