Functional outcome and SF-12 Case Report Form (CRF)-7 completion (Function & SF-12)	PHASE 2: At 6 months after randomization	REDCap application / surgeon or assistant
Case Report Form (CRF)-8 completion (Adverse Events)	PHASE 2: Assessed on a daily interval, during hospitalization(s), after IPAA and ostomy reversal surgery and then reassessed at 1-2 month intervals, until 6 months after IPAA.	REDCap application / surgeon or assistant

Clinical Adverse Event Reporting Form

Short versus long interval to loop ileostomy reversal after ileal pouch surgery in patients with ulcerative colitis (SLIRPS) trial

A randomized, prospective trial investigating the timing of diverting ileostomy closure after ileal j-pouch surgery.

Event ID: _____ Study Center: _____ Study ID: _____

Event Name: _____

DOB: ____ / ____ / ____-____ Gender: _____ Race: _____
mm dd yyyy

Name of MD Reporting Event?	_____
Date of Medical Review	____ / ____ / ____-____ mm dd yyyy
Is this a Serious Adverse Event (SAE)?	 Yes  No
Indicate all classifications(s) applicable	 Death  Life threatening  Disability  Congenital anomaly/birth defect  Hospitalization - Initial  Hospitalization - Prolongation  Other
Specify Other	_____
Relationship/Causality (likelihood that study agent caused the event)	 Not related  Probably not related  Possibly related  Related

Timing of Ileostomy Closure after Ileal Pouch Surgery

	Is the event Expected?
	Is the event Unexpected?

Timing of Ileostomy Closure after Ileal Pouch Surgery

MD Narrative:	

Measures at the onset of adverse event
 
 None
 
 Surgical Procedure
 
 Treatment with medication  Other
	
Specify Other:	

Outcome of event (sequelae are defined as conditions following and resulting from event)
 
 Recovered without sequelae
 
 Recovered with sequelae
 
 Not yet recovered
 
 Died
	
Signature of Study Center MD	
Date Form Completed	____ / ____ / ____ - ____ mm dd yyyy

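### SF-12 and pouch function carry two conflicting assessment dates, and the mixed-model rationale assumes repeated measurements that the schedule does not contain

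*Combined protocol and SAP*

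**What the plan says.** Three places date the assessment of SF-12 and pouch function.

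- Section 3, Overview of time sequence, item 8b: function and "quality of life (SF-12) will be assessed and recorded once at 6 months after ostomy reversal".
- Section 1, Secondary variables: quality of life is item 4 of the list, which ends "5) IPAA functional outcomes (all at 6 months after randomization".
- Appendix, Timeline study visits: CRF-7 has a single row, timed "At 6 months after randomization".

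The form list in section 9 places both outcomes on Form 7 only (the entry runs "Functional Outcome & SF-12; Form 8, Adverse Events"). The screening and operative data lists in section 4 contain no SF-12 or function item.

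On analysis, section 10 and the Summary carry the same sentence. Its reason is "Since the quality of life scales are continuous variables measured over time" and its conclusion is "we will compare the early vs. late closure groups for these outcomes using linear mixed models". Aim #2 in section 2 is "To compare the short vs. long interval groups on measures of health-related quality of life (SF-12) and IPAA functional outcomes". Neither section 10 nor the Summary gives an instrument, a scoring rule or a model for function.

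**The concern.** Two things do not fit together. First, the instructions to sites and the endpoint definition start the 6-month count from different events. The events are close together in the early arm and weeks apart in the late arm, so the conflict falls almost wholly on one arm. If sites follow item 8b, an arm difference in SF-12 or function mixes the effect of closure timing with time since surgery. A patient whose ileostomy is never closed has no assessment date at all.

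Second, the analysis is justified by repeated measurement, but the schedule provides one measurement. An analyst following section 10 literally would look for a time trend that the data cannot supply.

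Aim #2 and the quality-of-life half of the hypothesis rest on these data.

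**Working it through.** **Sample size.** The only sample size in the plan is for the CCI, the primary outcome. With a 10-point difference, SD 20-22, two-sided alpha 0.05 and 80% power, n per group = 2 × (1.96 + 0.8416)² × (SD/10)². This gives 2 × 7.849 × 4 = 62.8, so 63, and 2 × 7.849 × 4.84 = 75.98, so 76. Both match section 10. The present point does not touch them.

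**Inputs for timing.** Days are counted from pouch surgery (IPAA).

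- Randomization R: day 5-12 (section 3, item 6; Appendix).
- Early closure E: day 7-12, not before R (section 3, item 7a).
- Late closure L: 8-12 weeks, day 56-84 (section 3, item 7b).
- Screening: 0-30 days before IPAA (section 3).
- Assumption: 6 months = 183 days and 1 month = 30.44 days; the documents give no visit window.

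**Step 1: distance between the two dates.** This equals closure day minus randomization day.

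- Early: 0 (closed on the day of randomization) to 12 − 5 = 7 days.
- Late: 56 − 12 = 44 to 84 − 5 = 79 days.

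**Step 2: assessment day after IPAA.**

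| Count from | Early arm | Late arm |
|---|---|---|
| Reversal | 7 + 183 to 12 + 183 = 190-195 | 56 + 183 to 84 + 183 = 239-267 |
| Randomization | 5 + 183 to 12 + 183 = 188-195 | 188-195 |

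Counted from reversal, the arms are 56 − 12 = 44 to 84 − 7 = 77 days apart, and the ranges do not overlap.

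**Step 3: time since closure if counted from randomization.**

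- Early: 183 − 7 = 176 to 183 − 0 = 183 days.
- Late: 183 − 79 = 104 to 183 − 44 = 139 days.
- Difference: 176 − 139 = 37 to 183 − 104 = 79 days.

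**Step 4: comparison with the plan's own durations.** The Summary gives about 7 months per patient.

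- From screening, counting from randomization: 188 to 195 + 30 = 225 days, or 6.2-7.4 months, in both arms.
- From screening, counting from reversal: early 190-225 days, or 6.2-7.4 months; late 239 to 267 + 30 = 297 days, or 7.9-9.8 months.

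The Summary also states: "Phase 2 will have a duration of approximately 6 months and will begin after informed consent #2 is obtained". Consent #2 falls on day 5-12. Counting from reversal, the late-arm assessment comes 239 − 12 = 227 to 267 − 5 = 262 days later, or 7.5-8.6 months. Both durations are approximate. They favor randomization as the starting point in the late arm and cannot discriminate in the early arm.

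**Step 5: what one record per patient can support.** In a repeated-measures model the score is a group effect plus a patient effect u plus a residual e. With one score per patient, only Var(u) + Var(e) is identified, and no within-patient change is observed. At one common time after randomization, a time term is indistinguishable from the intercept. A hospital effect, fixed or random, can still be fitted, because hospitals contribute several patients.

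**The case against.** The strongest reply is that this is a drafting slip. Two of the three timing statements agree, the stated durations fit them, and linear mixed models can be fitted with hospital as a random effect. All of that stands. It limits the size of the point but does not remove it: item 8b is the operative instruction in the time sequence, and the reason given for the model is repetition over time, not clustering by hospital.

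A second reply is that equal time since closure is a legitimate target for pouch function, which would favor item 8b. That is fair. Counting from randomization leaves late-arm patients 37-79 fewer days since closure, and nothing in the documents shows that this is unimportant for function. The demonstrated error is the inconsistency; the choice of starting point is a recommendation with a real trade-off.

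Third, the word for a single assessment appears only in item 8b. For the randomization date, single completion is inferred from the one CRF-7 row and the absence of SF-12 elsewhere. CRF-6, by contrast, has six dated rows.

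A reader might also infer that the plan promises an intention-to-treat analysis of SF-12 that item 8b would break. The documents do not say so outright: section 10 states intention-to-treat for the primary analysis and describes secondary analyses as per-protocol and as-treated. The missing date for a patient never closed follows from item 8b alone.

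**Conclusion.** The point holds for secondary outcomes and should be fixed. The two timing instructions conflict, by 0-7 days in the early arm and 44-79 days in the late arm. The repeated-measures reason for the SF-12 model has no repeated measure behind it.

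The ranges assume closure within the stated windows and exactly 183 days. Section 10 itself expects complications that delay closure in the early arm, and section 3, item 6 and the Appendix give late closure with no upper limit. Either widens the gap.

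A reader might infer that Aim #2 cannot be answered, or that mixed models are impossible here. Neither follows. A comparison at one fixed time after randomization is valid without a baseline score, and a hospital random effect is estimable. The primary CCI analysis and the sample size are unaffected. The lack of a stated analysis for pouch function is missing detail, a smaller matter than the two contradictions.

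**What to change.** 1. Change section 3, item 8b to 6 months after randomization, matching the Summary and the Appendix, so that both arms are assessed at the same time after randomization. The cost is the shorter time since closure in the late arm, which may matter for function; report time since closure at assessment by arm so that readers can see it.
2. In section 10 and the Summary, replace the repeated-measures rationale with a between-group comparison of the 6-month SF-12 scores by randomized group, adjusted for hospital as a fixed or random effect.
3. As a minor addition, name the pouch-function measure and its scoring, state a single-time comparison by randomized group suited to its scale, and state how patients not closed at 6 months are counted.

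Items 1 and 2 are wording changes with no added visits or forms. Item 3 needs the sponsor to specify a measure.

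The differing late-closure windows in section 3 (items 6 and 7b) and the Appendix must also be reconciled by the sponsor. That is a separate point, and this review does not choose between them.

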Appendix

Table: Clavien-Dindo Classification (From Reference #1)

[figure not shown]
TABLE 1. Classification of Surgical Complications

Grade	Definition
Grade I	Any deviation from the normal postoperative course without the need for pharmacological treatment or surgical, endoscopic, and radiological interventions Allowed therapeutic regimens are: drugs as antiemetics, antipyretics, analgesics, diuretics, electrolytes, and physiotherapy. This grade also includes wound infections opened at the bedside
Grade II	Requiring pharmacological treatment with drugs other than such allowed for grade I complications Blood transfusions and total parenteral nutrition are also included
Grade III	Requiring surgical, endoscopic or radiological intervention
Grade IIIa	Intervention not under general anesthesia
Grade IIIb	Intervention under general anesthesia
Grade IV	Life-threatening complication (including CNS complications)* requiring IC/ICU management
Grade IVa	Single organ dysfunction (including dialysis)
Grade IVb	Multiorgan dysfunction
Grade V	Death of a patient
Suffix "d"	If the patient suffers from a complication at the time of discharge (see examples in Table 2), the suffix "d" (for "disability") is added to the respective grade of complication. This label indicates the need for a follow-up to fully evaluate the complication.

[figure not shown]
*Brain hemorrhage, ischemic stroke, subarachnoidal bleeding, but excluding transient ischemic attacks.
CNS, central nervous system; IC, intermediate care; ICU, intensive care unit.

Timing of Ileostomy Closure after Ileal Pouch Surgery

Illustrations:

2-stage IPAA with (loop) ileostomy

Timeline study visits

Procedure	Timing	Location and/or individual responsible
Inclusion/exclusion criteria assessment	PHASE 1: During IPAA preoperative assessment	Surgical outpatient clinic / Surgeon or trial assistant
Informed Consent #1: obtained from patients who meet initial inclusion and exclusion criteria		
Case Report Form (CRF)-1 completion (Screening)	PHASE 1: During IPAA preoperative assessment	Surgical outpatient clinic / Surgeon or trial assistant
Case Report Form (CRF)-2 completion (Pre-IPAA details)	PHASE 1: Within 2 days of IPAA	REDCap application / Surgeon or trial assistant
IPAA surgery	PHASE 1: At discretion of patient and surgeon and within 30 days of inclusion/exclusion criteria assessment	Study site operating room / surgeon
Case Report Form (CRF)-3 completion (IPAA surgery details)	PHASE 1: Within 2 days of IPAA surgery	REDCap application / surgeon or assistant
Post-IPAA clinical assessment	PHASE 1: Day 5 to 12 after IPAA	Study site inpatient setting / Surgeon
Exclusion of potential study patients judged not clinically suitable for trial entry. Case Report Form (CRF)-4 (IPAA Assessment)	PHASE 1: Day 5 to 12 after IPAA	REDCap application / Study site inpatient setting / Surgeon
Informed Consent #2 - obtained only from potential study patients who are clinically suitable for early ileostomy reversal	PHASE 2: Day 5 to 12 after IPAA, after IPAA clinical assessment	Study site inpatient setting / Surgeon
Radiologic imaging assessment of the IPAA	PHASE 2: Day 5 to 12 days after IPAA	Study site radiology suite
Case Report Form (CRF)-4 completion (IPAA Assessment) - finish	PHASE 2: Day 5 to 12 after IPAA, after IPAA radiological assessment	REDCap application / Study site inpatient setting / Surgeon
Randomization - of study patients who are radiologically suitable for early ileostomy closure	PHASE 2: Day 5 to 12 days after IPAA	Study site trial coordinator office / trial assistant
Ileostomy Closure	PHASE 2: Experimental Arm: 7 to 12 days after IPAA surgery Control Arm: \geq 8 weeks after IPAA surgery	Study site operating room

Timing of Ileostomy Closure after Ileal Pouch Surgery

Case Report Form (CRF)-5 completion (ostomy reversal details)	PHASE 2: Within 2 days of ostomy closure	REDCap application / surgeon or assistant
Outcome Assessment #1- Case Report Form (CRF)-6 (complications)	PHASE 2: 0-1 month after randomization.	REDCap application / surgeon or assistant
Outcome Assessment #2- Case Report Form (CRF)-6 (complications)	PHASE 2: 1-2 months after randomization.	REDCap application / surgeon or assistant
Outcome Assessment #3- Case Report Form (CRF)-6 (complications)	PHASE 2: 2-3 months after randomization.	REDCap application / surgeon or assistant
Outcome Assessment #4- Case Report Form (CRF)-6 (complications)	PHASE 2: 3-4 months after randomization.	REDCap application / surgeon or assistant
Outcome Assessment #5- Case Report Form (CRF)-6 (complications)	PHASE 2: 4-5 months after randomization.	REDCap application / surgeon or assistant
Outcome Assessment #6- Case Report Form (CRF)-6 (complications)	PHASE 2: 5-6 months after randomization.	REDCap application / surgeon or assistant
Functional outcome and SF-12 Case Report Form (CRF)-7 completion (Function & SF-12)	PHASE 2: At 6 months after randomization	REDCap application / surgeon or assistant
Case Report Form (CRF)-8 completion (Adverse Events)	PHASE 2: Assessed on a daily interval, during hospitalization(s), after IPAA and ostomy reversal surgery and then reassessed at 1-2 month intervals, until 6 months after IPAA.	REDCap application / surgeon or assistant

Clinical Adverse Event Reporting Form

Short versus long interval to loop ileostomy reversal after ileal pouch surgery in patients with ulcerative colitis (SLIRPS) trial

A randomized, prospective trial investigating the timing of diverting ileostomy closure after ileal j-pouch surgery.

Event ID: _____ Study Center: _____ Study ID: _____

Event Name: _____

DOB: ____ / ____ / ____-____ Gender: _____ Race: _____
mm dd yyyy

Name of MD Reporting Event?	_____
Date of Medical Review	____ / ____ / ____-____ mm dd yyyy
Is this a Serious Adverse Event (SAE)?	 Yes  No
Indicate all classifications(s) applicable	 Death  Life threatening  Disability  Congenital anomaly/birth defect  Hospitalization - Initial  Hospitalization - Prolongation  Other
Specify Other	_____
Relationship/Causality (likelihood that study agent caused the event)	 Not related  Probably not related  Possibly related  Related

Timing of Ileostomy Closure after Ileal Pouch Surgery

	Is the event Expected?
	Is the event Unexpected?

Timing of Ileostomy Closure after Ileal Pouch Surgery

MD Narrative:	

Measures at the onset of adverse event
 
 None
 
 Surgical Procedure
 
 Treatment with medication  Other
	
Specify Other:	

Outcome of event (sequelae are defined as conditions following and resulting from event)
 
 Recovered without sequelae
 
 Recovered with sequelae
 
 Not yet recovered
 
 Died
	
Signature of Study Center MD	
Date Form Completed	____ / ____ / ____ - ____ mm dd yyyy

Lead Study Principal Investigator assessment:

Does this event suggests that the research places subjects or others at greater risk of physical or psychological harm than was previously known or recognized?

Yes No

Within 5 days of knowledge of event please email:

[contact]

[contact]
